7.3.3. Adverse Events Reporting

AEs will be reported by the subjects (or, when appropriate, by a caregiver, surrogate, or the subject's legally authorized representative).

The investigator and any qualified designees are responsible for detecting, documenting, and recording events that meet the definition of an AE or SAE and remain responsible to pursue and obtain adequate information both to determine the outcome and to assess whether the event meets the criteria for classification as an SAE or caused the subject to discontinue the study intervention (see Section 6.1).

Each subject/parent(s)/legal guardian will be questioned about the occurrence of AEs in a nonleading manner.

In addition, the investigator may be requested by the PTC Pharmacovigilance Department to obtain specific follow-up information in an expedited fashion.

All AEs are to be recorded in the source documents and on the eCRF using concise medical terminology; whenever possible, terms contained in the Medical Dictionary for Regulatory

Activities (MedDRA) should be employed. In addition, the following information should be recorded:

- Indication of whether the event is serious or nonserious (see Section 7.3.2)
- Relationship to study intervention (see Section 7.3.5)
- Severity of the event (see Section 7.3.5)
- Onset date
- Resolution date, or date of death
- Action taken
- Outcome of the event

Table 6 below summarizes the investigator site requirements for recording AEs on the eCRF and for reporting SAEs, adverse events of special interest (AESI) on the SAE Report Form to the PTC Pharmacovigilance Department.

Table 6: Investigator Site Requirements for Recording/Reporting Adverse Events

| Event | Recorded on the eCRF | Reported to the PTC Pharmacovigilance Department Within 24 Hours of Awareness |
|----------------------------------|-------------------------|---|
| Serious AE | All | All |
| Nonserious AE | All | None |
| Other, eg, exposure to the study | All (regardless of | All |
| intervention during pregnancy or | whether associated with | (regardless of whether associated with |
| breastfeeding | an AE) | an AE) |
| AESI | Not applicable | Not applicable |

Abbreviations: AE, adverse event, AESI, adverse event of special interest, eCRF, electronic care report form

7.3.4. Time Period and Frequency for Collecting Adverse Event and Serious Adverse Event Information

The AE (both serious and nonserious) collection and reporting period begins with the signing of the ICF and continues until 30 days after the last dose of study medication. All AEs during this time period must be recorded, whether or not the event is considered drug related.

For subjects who are screen failures, the active collection period for AEs ends when screen failure status is determined. Any SAEs occurring during screening procedures, should have the appropriate completed causality assessment (ie, "not related" to study intervention) section of the SAE Report Form completed.

If the subject withdraws from the study and also withdraws consent for the collection of future information, the active collection period for AEs ends when consent is withdrawn.

Investigators are not obligated to actively seek information on AEs or SAEs after conclusion of the study participation. However, if the investigator learns of any SAE, including a death, at any time after a subject has been discharged from the study, and he/she considers the event to be reasonably related to the study intervention, the investigator must promptly notify PTC Pharmacovigilance Department via the SAE Report Form.

7.3.4.1. Serious Adverse Event Reporting

All SAEs (both initial and follow-up) should be reported via the SAE Report Form to the PTC Pharmacovigilance Department immediately and under no circumstance should this exceed 24 hours from awareness. In addition, the AE portion of the eCRF must also be completed.

The SAE Report Form must be signed by the investigator; however, if the investigator is unable to sign at the time of the event or within 24 hours, the form should be signed by the clinical staff member reporting the SAE (eg, the study coordinator). The SAE Report Form must be faxed or emailed to the PTC Pharmacovigilance Department and to the site IRB/IEC (if required by local regulations) within 24 hours. The investigator's signature must be obtained as soon as possible after the report is submitted and the report revised if necessary, and submitted to the PTC Pharmacovigilance Department. The investigator will maintain a copy of the SAE Report Form on file at the study site.

Follow-up information to the SAE should be clearly documented as "follow-up" in the SAE Report Form and must also be faxed or emailed to the same party within the same timelines. All follow-up SAE Report Forms for the event must be signed by the investigator as per instructions above. Any source documents (eg, progress notes, nurses' notes, laboratory and diagnostic test results, discharge summaries) provided to the PTC Pharmacovigilance Department should be redacted so that the subject's name, address, and other personal identity information are obscured. Only the subject's study number and initials are to be provided (in regions where the provision of such information is permitted). The information in the AE portion of the eCRF and the SAE Report Form(s) must match or be reconciled. Where the same data are collected, the forms must be completed in a consistent manner. For example, the same AE term should be used on both forms.

The PTC Pharmacovigilance Department contact information for reporting SAEs is provided below. This information is also provided in the SAE Report Form:

PTC Pharmacovigilance Department Email: [contact] SAE FAX Line: [contact]

7.3.5. Method of Detecting Adverse Events and Serious Adverse Events

Care will be taken not to introduce bias when detecting AEs and/or SAEs. Open-ended and nonleading verbal questioning of the subject is the preferred method to inquire about AE occurrences.

7.3.5.1. Assessments of Severity of Adverse Events

The severity of AEs will be graded using the Common Terminology Criteria for Adverse Events (CTCAE) Version 5.0. For each episode, the highest severity grade attained should be reported.

The investigator will make an assessment of severity for each AE and SAE reported during the study and assign it to 1 of the following categories (Table 7).

Table 7: Grading of Adverse Events

| Grade | Adjective | Description |
|-------|------------------|--|
| 1 | Mild | Asymptomatic or mild symptoms; clinical or diagnostic observations only; intervention not indicated. |
| 2 | Moderate | Minimal, local, or noninvasive intervention indicated, limiting age appropriate instrumental Activities of Daily Living (ADL). Instrumental ADL refers to preparing meals, shopping for groceries or clothes, using the telephone, managing money, etc. |
| 3 | Severe | Severe or medically significant but not immediately life-threatening; hospitalization or prolongation of hospitalization indicated; disabling, limiting self-care ADL. Self-care ADL refers to bathing, dressing, and undressing, feeding self, using the toilet, taking medications, and not bedridden. |
| 4 | Life-threatening | Sign or symptom results in urgent intervention. |
| 5 | Fatal | Sign or symptom results in death. |

7.3.5.2. Describing Adverse Event Relationship to Study Intervention

The investigator should provide an assessment of the relationship of the AE/SAE to the study intervention and each occurrence of each AE/SAE outlined in Table 8. The investigator will use clinical judgment to determine the relationship.

The investigator will also consult the IB and/or product information, for marketed products, in his/her assessment.

For each AE/SAE, the investigator must document in the medical notes that he/she has reviewed the AE/SAE and has provided an assessment of causality.

There may be situations in which an AE/SAE has occurred, and the investigator has minimal information to include in the initial SAE Report Form to the PTC Pharmacovigilance Department. However, it is very important that the investigator always make an assessment of causality for every event before the initial transmission of the SAE Report Form to the PTC Pharmacovigilance Department.

The investigator should decide whether, in his or her medical judgment, there is a reasonable possibility that the event may have been caused by the investigational product.

- If no valid reason exists for suggesting a relationship, then the AE should be classified as "unrelated." If a relationship cannot be excluded but there is a clear alternate cause that is more likely to have caused the AE than the study intervention, the AE should be considered "unlikely related."
- If there is any valid reason, even if undetermined, for suspecting a possible cause-and-effect relationship between the investigational product and the occurrence of the AE, then the AE should be considered "possibly or probably related."

If the relationship between the AE/SAE and the investigational product is determined to be "possible" or "probable," the event will be considered related to the investigational product for the purposes of expedited regulatory reporting. An assessment of "unlikely related" will be considered unrelated for regulatory reporting purposes.

The investigator may change his/her opinion of causality in light of follow-up information and must send an SAE follow-up report with the updated causality assessment.

The causality assessment is 1 of the criteria used when determining regulatory reporting requirements (Table 8).

Table 8: Relationship of Study Intervention to Adverse Event

| Relationship | Description |
|--------------|--|
| Probably | A clinical event in which a relationship to the study drug seems probable because of such factors as consistency with known effects of the drug; a clear temporal association with the use of the drug; improvement upon withdrawal of the drug; recurrence upon rechallenge with the drug; lack of alternative explanations for the event. |
| Possible | A clinical event occurring coincident with administration of the study intervention, and which may or may not be explained by concurrent disease or other drugs or chemicals. Information on drug withdrawal or rechallenge may be lacking. |
| Unlikely | A clinical event with a temporal relationship to the study intervention exposure that does not preclude causality but for which there is a clear alternate cause that is more likely to have caused the adverse event than the study intervention. Such alternatives include a concomitantly administered drug, the subject's disease state, other medical conditions, or environmental factors. |
| Unrelated | A clinical event for which a relationship to the study intervention seems improbable because of factors such as inconsistency with known effects of the study intervention, lack of a temporal association with study drug administration, lack of association of the event with study intervention withdrawal or rechallenge, and/or presence of alternative explanations for the event. Alternative explanations might include a known relationship of the adverse event to a concomitant drug, medical history of a similar event, the subject's disease state, other medical conditions, or environmental factors. |

7.3.6. Treatment of Adverse Events and Serious Adverse Events

Treatment of AEs and SAEs will be symptom-based and at the discretion of the investigator.

7.3.7. Follow-Up of Adverse Events and Serious Adverse Events

After the initial AE/SAE report, the investigator is required to proactively follow each subject at subsequent visits/contacts. All AEs will be followed until resolution, stabilization, the event is otherwise explained, or the subject is lost to follow-up (as defined in Section 6.3).

All AEs should be followed up by the investigator until they are resolved or the investigator assesses them as chronic or stable. The investigator should consider protocol guidelines and use his/her discretion in ordering additional tests as necessary to monitor the resolution of such events. In the event of additional investigations, the PTC Pharmacovigilance Department should be informed via email or fax.

A subject withdrawn from the study because of an AE must be followed by the investigator until clinical recovery is complete and laboratory results have returned to normal, or until progression has been stabilized. Follow-up may need to continue after the subject has discontinued from the study, and additional investigations may be requested by the medical monitoring team.

The investigator must submit any updated SAE information to the PTC Pharmacovigilance Department within 24 hours of receipt of the information.

7.3.8. Regulatory Reporting Requirements for Serious Adverse Events

Prompt notification by the investigator to PTC of an SAE is essential so that legal obligations and ethical responsibilities toward the safety of subjects and the safety of a study intervention under clinical investigation are met.

As the sponsor of the study, PTC has a legal responsibility to notify the local regulatory authority and other regulatory agencies about the safety of a study intervention under clinical investigation. PTC will comply with country-specific regulatory requirements relating to safety reporting to the regulatory authority, institutional review boards (IRBs)/independent ethics committees (IECs), and investigators.

Investigator safety reports must be prepared for suspected unexpected serious adverse reactions (SUSARs) according to local regulatory requirements and sponsor policy and forwarded to investigators as necessary.

An investigator who receives SUSAR or other safety-specific information (eg, summary or listing of SAEs) from PTC will review and then file it along with the reference document and will notify the IRB/IEC, if appropriate according to local requirements.

7.3.9. PTC Expedited Reporting of SUSARs to EudraVigilance

In the EU, as per requirements of EU Clinical Trials Regulation No. 536/2014 of the European Parliament and of the Council of 16 April 2014 on Clinical Trials on Medicinal Products for Human Use, and Repealing Directive 2001/20/EC, SUSARs should be submitted to the EudraVigilance database. Additional direct submissions from the Sponsor to Ethics Committees and National Competent Authorities are not required.

As per the EU Clinical Trials Regulation, the Sponsor shall notify the Member States concerned of all findings which affect the benefit-risk balance of the medicinal product or clinical trial, and any urgent safety measures (USMs) taken. The Sponsor will submit findings that affect the benefit-risk balance or any USM via the Clinical Trials Information System (CTIS).

7.3.10. Exposure During Pregnancy or Breastfeeding

Exposure to the study intervention under study during pregnancy or breastfeeding are reportable to the PTC Pharmacovigilance Department within 24 hours of investigator awareness.

7.3.10.1. Exposure During Pregnancy

PTC Pharmacovigilance Department must be notified in the event that a female subject in the study, or a female partner of a male subject in the study, becomes pregnant on-study or within 90 days of the last dose of the study intervention on an Investigational and Marketed Products Pregnancy Report Form (hereafter referred to as Pregnancy Report Form) (see study manual for details). This must be reported whether or not an AE has occurred and within 24 hours of awareness of the pregnancy. The information submitted should include the anticipated date of birth or pregnancy termination.

Written consent is required prior to collecting and reporting any information on a female partner of a male subject in the study.

In any of the 4 situations listed below, the subject will be provided with a Pregnancy/Pregnant Partner Data Release Form to request their consent to follow the progress of the pregnancy and the birth and the health of their child.

- Subject becomes pregnant while participating in the study.
- Female partner of a male subject participating in the study becomes pregnant.
- Subject becomes pregnant up to 30 days after completion of the study.
- Female partner of a male subject participating in the study becomes pregnant up to 90 days after the partner completed the study.

Because the risk to an unborn child is unknown, the subject should be asked to sign the Pregnancy/Pregnant Partner Release Form. However, signing this form is voluntary; it is up to the subjects to decide whether to agree to the collection of this information or not. Upon signing, the subject's and the child's medical records relating to the pregnancy and delivery, and the health of the child, will be reviewed for up to 1 year of age.

If possible, the investigator should follow the subject, or the pregnant female partner of a male subject, until completion of the pregnancy and notify the PTC medical monitor of the outcome within 5 days or as specified below. The investigator must provide this information as a follow-up to the initial Pregnancy Report Form via the Pregnancy Outcome Section (see the study manual for details).

If the outcome of the pregnancy meets the criteria for immediate classification as an SAE (ie, spontaneous abortion, stillbirth, neonatal death, or congenital anomaly [including that in an aborted fetus]), the investigator should follow the procedures for reporting SAEs (ie, report the event to PTC Pharmacovigilance Department and follow-up by completion of appropriate AE eCRFs and submission of the SAE Report Form).

All information collected with regard to the pregnancy, delivery of the child, and the health of the child is confidential to the limit allowed by law. These data will be coded to hide the subject's identity and the identity of the child. In particular, the subject's name and the child's name will not be reproduced on any other paper or electronic document. These data will not be disclosed voluntarily by PTC. However, regulatory agencies may have to examine these data to ensure that the study is done properly.

Of note, if the pregnant female partner of a male study subject participating in the study does not wish to provide such information, this will not prevent the partner from continuing with the study.

Any female subject who becomes pregnant while participating in the study will discontinue study intervention/withdrawn or be excluded from the study (see Section 4.3).

7.3.10.2. Exposure During Breastfeeding

An exposure during breastfeeding occurs if:

• A female subject is found to be breastfeeding while receiving or up to 30 days after discontinuing study intervention.

 A female is found to be breastfeeding while being exposed or having been exposed to study intervention (ie, environmental exposure). An example of environmental exposure during breastfeeding is a female family member or healthcare provider who reports that she is breastfeeding after having been exposed to the study intervention by inhalation or skin contact.

The investigator must report exposure during breastfeeding to the PTC Pharmacovigilance Department within 24 hours of the investigator's awareness, irrespective of whether an SAE has occurred. The information must be reported using the Pregnancy Report Form. When exposure during breastfeeding occurs in the setting of environmental exposure, the exposure information does not pertain to the subject enrolled in the study, so the information is not recorded on an eCRF. However, a copy of the completed Pregnancy Report Form is maintained in the investigator site file. An exposure during breastfeeding report is not created when a PTC drug specifically approved for use in breastfeeding women (eg, vitamins) is administered in accordance with authorized use. However, if the infant experiences an SAE associated with such a drug, the SAE is reported together with the exposure during breastfeeding via SAE Report Form.

7.3.11. Disease-Related Events and/or Disease-Related Outcomes Not Qualifying as AEs or SAEs

Not applicable.

7.3.11.1. Progression of Underlying Disease

If the progression of the underlying disease is greater than that which would normally be expected, or if the investigator considers that there may be a causal relationship between the investigational medicinal product or protocol design/procedures and the disease progression, then it must be reported to the PTC Pharmacovigilance Department within 24 hours of awareness.

7.3.11.2. Abnormal Findings Associated with the Disease Being Studied

Clinically significant abnormal laboratory findings or other abnormal assessments that are detected during the study or are present at baseline and significantly worsen following the start of the study will be reported as AEs or SAEs. However, clinically significant abnormal laboratory findings or other abnormal assessments that are associated with the disease being studied, unless judged by the investigator as more severe than expected for the subject's condition, or that are present or detected at the start of the study and do not worsen, should not be reported as AEs or SAEs.

7.3.12. Contraceptive Guidance

7.3.12.1. Male Participant Reproductive Inclusion Criteria

Male subjects are eligible to participate if they agree to the following requirements during the intervention period and for at least 90 days after the last dose of study intervention, which corresponds to the time needed to eliminate reproductive safety risk of the study intervention(s):

• Refrain from donating sperm.

PLUS, either:

• Be abstinent from heterosexual intercourse with a female of childbearing potential as their preferred and usual lifestyle (abstinent on a long-term and persistent basis) and agree to remain abstinent.

OR

- Must agree to use a male condom when engaging in any activity that allows for passage of ejaculate to another person.
- In addition to male condom use, a highly effective method of contraception may be considered in WOCBP partners of male subjects (refer to the list of highly effective methods below in Section 7.3.12.4).

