A subset of approximately 36 subjects from select sites participating in the PK Sub-Study will participate in serial blood sampling to characterize the PK of PTC857 in subjects with ALS.

Diagnosis and Main Criteria for Inclusion:

Individuals eligible to participate in this study include those who meet all the inclusion criteria at both the Screening Visit and the Baseline Visit, unless otherwise stated:

- 1. Males or females aged between 18 and 80 years at the time of the initial Screening Visit
- 2. ALS with preserved function, defined as:
 - a. Onset of the first symptom leading to the diagnosis of ALS ≤24 months at the time of the initial Screening Visit
 - b. Revised El Escorial criteria of either:
 - (i) Clinically definite ALS
 - (ii) Clinically probable ALS
- 3. A total ALSFRS-R score of at least 34 at the start of the Screening Period
- 4. No significant respiratory compromise as evidenced by slow vital capacity ≥60% at the start of the Screening Period (refer to the laboratory manual for specific requirements)
- 5. Subjects or their designee (ie, legal authorized representative or caregiver) must understand the nature of the study and must provide signed and dated written informed consent prior to conducting any study-related procedures
- 6. Females must be either postmenopausal for ≥1 year (cessation of menses for 12 consecutive months) or surgically sterile (having undergone tubal ligation, hysterectomy, or bilateral oophorectomy) for at least 6 months or, if of childbearing potential and not abstinent, willing to use a highly effective method of contraception

- from the start of the Screening Period through 90 days after the last dose of study drug. Females who are abstinent will not be required to use a contraceptive method unless they become sexually active
- 7. Females must refrain from ova (egg cell) donation from the start of the Screening Period through 90 days after the last dose of study drug
- 8. Males, if not surgically sterilized, with female partners of childbearing potential must agree to use barrier contraceptive (ie, condom) and their female partners must use a highly effective method of contraception from the start of the Screening Period through 90 days after the last dose of study drug
- 9. Males must refrain from sperm donations from the start of the Screening Period through 90 days after the last dose of the study drug
- 10. Willing and able to comply with all protocol procedures

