4.2. Inclusion Criteria

Individuals eligible to participate in this study include those who meet all the inclusion criteria at both the Screening Visit and the Baseline Visit, unless otherwise stated:

- 1. Males or females aged between 18 and 80 years at the time of the initial Screening Visit
- 2. ALS with preserved function, defined as:
 - a. Onset of the first symptom leading to the diagnosis of ALS ≤24 months at the time of the initial Screening Visit
 - b. Revised El Escorial criteria of either:
 - Clinically definite ALS
 - Clinically probable ALS
- 3. A total ALSFRS-R score of at least 34 at the start of the Screening Period
- 4. No significant respiratory compromise as evidenced by slow vital capacity ≥60% at the start of the Screening Period (refer to the laboratory manual for specific requirements)
- 5. Subjects or their designee (ie, legal authorized representative or caregiver) must understand the nature of the study and must provide signed and dated written informed consent prior to conducting any study-related procedures
- 6. Females must be either postmenopausal for ≥1 year (cessation of menses for 12 consecutive months) or surgically sterile (having undergone tubal ligation, hysterectomy, or bilateral oophorectomy) for at least 6 months or, if of childbearing potential and not abstinent, willing to use a highly effective method of contraception from the start of the Screening Period through 90 days after the last dose of study drug. Females who are abstinent will not be required to use a contraceptive method unless they become sexually active
- 7. Females must refrain from ova (egg cell) donation from the start of the Screening Period through 90 days after the last dose of study drug
- 8. Males, if not surgically sterilized, with female partners of childbearing potential must agree to use barrier contraceptive (ie, condom) and their female partners must use a highly effective method of contraception from the start of the Screening Period through 90 days after the last dose of study drug
- 9. Males must refrain from sperm donations from the start of the Screening Period through 90 days after the last dose of the study drug
- 10. Willing and able to comply with all protocol procedures

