1.4.1. Inclusion Criteria

Individuals eligible to participate in this study include those who meet all the inclusion criteria at both the Screening Visit and the Baseline Visit, unless otherwise stated:

- 1. Males or females aged between 18 and 80 years at the time of the initial Screening Visit
- 2. ALS with preserved function, defined as:
 - Onset of the first symptom leading to the diagnosis of ALS ≤24 months at the time of the initial Screening Visit
 - Revised El Escorial criteria of either:
 - i. Clinically definite ALS
 - ii. Clinically probable ALS
- 3. A total ALSFRS-R score of at least 34 at the start of the Screening Period

- 4. No significant respiratory compromise as evidenced by slow vital capacity ≥60% at the start of the Screening Period
- 5. Subjects or their designee (i.e., legal authorized representative or caregiver) must understand the nature of the study and must provide signed and dated written informed consent prior to conducting any study-related procedures.
- 6. Females must be either postmenopausal for ≥1 year (cessation of menses for 12 consecutive months) or surgically sterile (having undergone tubal ligation, hysterectomy, or bilateral oophorectomy) for at least 6 months or, if of childbearing potential and not abstinent, willing to use a highly effective method of contraception from the start of the Screening Period through 90 days after the last dose of study drug. Females who are abstinent will not be required to use a contraceptive method unless they become sexually active.
- 7. Females must refrain from ova (egg cell) donation from the start of the Screening Period through 90 days after the last dose of study drug.
- 8. Males, if not surgically sterilized, with female partners of childbearing potential must agree to use barrier contraceptive (i.e., condom) and their female partners must use a highly effective method of contraception from the start of the Screening Period through 90 days after the last dose of study drug.
- 9. Males must refrain from sperm donations from the start of the Screening Period through 90 days after the last dose of study drug.
- 10. Willing and able to comply with all protocol procedures.
- 11. Willing and able to swallow study drug (oral solution) at randomization.

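### Section 7.3.12.1 makes partner contraception optional where inclusion criterion 8 makes it mandatory; a smaller timing mismatch affects the pregnancy release form

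*Protocol*

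**What the plan says.** **Partner contraception.** Criterion 8 in Protocol Section 4.2 begins "Males, if not surgically sterilized, with female partners of childbearing potential must agree to use barrier contraceptive" and continues "their female partners must use a highly effective method of contraception from the start of the Screening Period". The obligation lasts until 90 days after the last dose. The synopsis carries the same criterion ("must agree to use barrier contraceptive (ie, condom) and their female partners must use a highly effective method of contraception"), as does SAP Section 1.4.1 ("must agree to use barrier contraceptive (i.e., condom) and their female partners must use a highly effective method of contraception"). Section 4.2 opens with the rule that "Individuals eligible to participate in this study include those who meet all the inclusion criteria at both the Screening Visit and the Baseline Visit".

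Section 7.3.12.1 also sets conditions under which men may take part. They must "agree to the following requirements during the intervention period and for at least 90 days after the last dose of study intervention". Besides not donating sperm, a man chooses between abstinence and condom use. Under the condom route, the section adds that "a highly effective method of contraception may be considered in WOCBP partners of male subjects".

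**Pregnancy follow-up.** Section 7.3.10.1 makes a pregnancy reportable within 24 hours of awareness if it begins on-study or in the 90 days after the last dose. It then lists four situations in which a data-release form is provided. For a female subject, these are pregnancy during participation and pregnancy up to 30 days after she completes the study. For a male subject's partner, the later limit is 90 days after he completes it.

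**The concern.** For the same couples over the same months, one section compels a reproductive-safety measure and another leaves it to discretion. Section 7.3.12.1 cannot be read as mere background, because its heading and opening sentence present it as eligibility text. A site that counsels from it would tell partners that a required method is optional. The subject would then fall short of an inclusion criterion, and Section 10.1 treats deviations that affect eligibility as major.

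The form mismatch is smaller. The form asks for consent to follow the pregnancy and the child, and signing it opens the records of mother and child until the child is 1 year old. For some reportable pregnancies in female subjects, none of the four listed situations prompts the site to offer it.

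**Working it through.** No power or alpha figure is involved. Part 1 compares texts; Part 2 counts days.

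**Part 1: partner contraception**

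| Item | Criterion 8, Section 4.2 | Section 7.3.12.1 |
|---|---|---|
| Highly effective method for the partner | Must | May |
| Start | Screening | Intervention period |
| End | 90 days after last dose | At least 90 days after last dose |
| Condom | Required if the partner can conceive | Required more widely, unless abstinent |
| Abstinence route | Not offered | Offered |

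The two texts overlap for a sexually active man who is not sterilized and whose partner can conceive, from first dose to 90 days after the last. For that couple, 'must' and 'may' cannot both be right. The opening rule of Section 4.2 settles which one binds: all its criteria have to be met, so criterion 8 does.

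The start dates differ by the length of Screening. This is scheduled from Day -56 (±5 days), so it is nominally 56 days, all before any study drug. It is not a firm bound: the protocol calls the length approximate and allows an extension for women who need longer to complete breast imaging. Women face the same mismatch. Criterion 6 requires that they be "willing to use a highly effective method of contraception from the start of the Screening Period through 90 days after the last dose", while Section 7.3.12.2 starts at the intervention period.

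**Part 2: release-form trigger for a female subject**

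Inputs:
- Reporting window: 90 days after last dose (Section 7.3.10.1).
- Form trigger: 30 days after completion for a subject, 90 days for a partner (Section 7.3.10.1).
- Follow-up call: 28 ±3 days after last dose (Section 3.2).
- For a woman who does not continue into the next part, the call completes the part (Section 3.6). Completion of the study is not defined for an individual.

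Let s be the days from last dose to completion. The trigger ends on Day s + 30, so the gap to Day 90 is max(0, 90 - (s + 30)) = max(0, 60 - s).

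| s (days) | Trigger ends | Gap (days) | Reading |
|---|---|---|---|
| 25 | Day 55 | 35 | Call at early edge of window |
| 28 | Day 58 | 32 | Call on schedule |
| 31 | Day 61 | 29 | Call at late edge of window |
| 60 or more | Day 90 or later | 0 | Stays in the study after stopping drug, as Section 6.4 encourages |
| 0 | Day 30 | 60 | Only if leaving at last dose is assumed to count as completion |

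The gap is also 0 for nearly all women if completion means the end of the whole study in Section 3.6. The partner trigger ends on Day s + 90, which is Day 118 at s = 28 (115 to 121), and leaves no gap for any s.

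If the trigger instead ends on Day max(s + 30, 90), the gap is 0 for every s and coverage is never shorter than now.

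**The case against.** **'May' forbids nothing.** A site that follows criterion 8 also satisfies 7.3.12.1, and criterion 8 binds. This stands for eligibility. A reader might infer that the protocol admits couples without partner contraception; it does not. What remains is the risk of wrong counselling. The public documents do not include the consent pages or the study manual, so that risk cannot be shown to have materialized.

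**The criterion is one text copied.** The synopsis, Section 4.2 and the SAP are not three independent statements. The SAP's list is also out of date: it keeps a criterion on swallowing the study drug that the current protocol lacks. This stands, and nothing here rests on a count of places.

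**Section 7.3.10.1 largely covers itself.** It does not call the four situations exclusive. It says without a time limit that the subject should be asked to sign, and it asks for follow-up to the end of the pregnancy where possible. A reader might infer that pregnancies after about Day 58 go unreported or cannot be followed. The documents do not support that: the notification duty runs the full 90 days. The mismatch is a drafting fault in one bullet.

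**The 60-day gap.** Section 3.6 ties completion to a final visit or call, so a gap of 60 days needs the added assumption shown in the table. Early leavers who consent to continued contact are followed about every 28 days (Table 1, note d). If that counts as staying in the study, it often removes the gap.

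**Section 7.3.12 is not looser overall.** It is stricter on hormonal confirmation of menopause and on condom use. The label in 7.3.12.4 suggests that less effective methods are allowed, but no weaker method is shown to be admitted.

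**Few people and limited signals.** ALS is typically diagnosed at 50 to 60 years (Section 1.5.2). Genotoxicity tests were negative, and the rat fertility study showed no effect on reproductive parameters (Section 1.4.1). Against this, eligibility starts at 18, a man's age does not settle whether his partner can conceive, and Section 7.3.10.1 itself treats the risk to a fetus as unknown.

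**Conclusion.** Section 7.3.12.1 is wrong as written: it makes optional what criterion 8 requires, and it starts later. Criterion 8 governs, so the eligibility rule itself is sound and the exposure is to miscounselling.

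The release-form mismatch is real but minor. For a woman who completes with the 4-week call, the gap is 32 days (29 to 35). This rests on reading completion as that call.

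The priority is low. Alpha, power and the efficacy analyses are unaffected.

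**What to change.** - **Section 7.3.12.1:** replace 'may be considered' with 'must be used' for WOCBP partners of men who are not surgically sterilized, and start the period at Screening as in criterion 8. Keep the condom rule and the abstinence route. Criterion 8 has no abstinence route, so that difference would remain.
- **Section 7.3.10.1, female-subject bullet:** let the form trigger run to the later of 30 days after completion of the study or 90 days after the last dose.
- **Editorial only:** in 7.3.12.2, call the required method 'highly effective' rather than 'acceptable' and start at Screening as in criterion 6. In 7.3.12.4, delete the parenthesis describing the list as a mix of highly and non-highly effective methods. Keep the hormonal confirmation of menopause.

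The cost is a wording amendment and a note to sites, with ethics submission and re-approval as local rules require (Section 11.1). No procedure, visit or analysis is added.
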